6.3.1.1. Incidence of Adverse Events

An overall summary of unsolicited TEAEs including the number and percentage of subjects who experience the following will be presented:

- Any unsolicited TEAEs
- Any serious TEAEs
- Any fatal TEAEs
- Any unsolicited medically-attended TEAEs
- Any unsolicited TEAEs leading to discontinuation from participation in the study
- Any unsolicited severe TEAEs
- Any unsolicited AESIs
- Any unsolicited non-serious TEAEs
- Any unsolicited severe non-serious TEAEs

The table will also include number and percentage of subjects with unsolicited TEAEs that are treatment-related per PI's assessment in each of the above categories.

In addition, separate listings containing individual subject adverse event data for unsolicited AEs, unsolicited TEAEs leading to discontinuation from participation in the study, serious AEs and fatal unsolicited AEs will be provided separately.

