7.1.5. Physical Examinations

A full physical examination, including height and weight, will be performed at Day 1 as indicated in the SoE ([Table 17](#), [Table 18](#), [Table 19](#), and [Table 20](#)). The full examination will include assessment of skin, head, ears, eyes, nose, throat, neck, thyroid, lungs, heart, cardiovascular system, abdomen, lymph nodes, and musculoskeletal system and extremities. Any clinically significant finding identified during a study visit should be reported as an MAAE.

Symptom-directed physical examinations may be performed at other time points at the discretion of the investigator. On the day of vaccination, before injection, the arm receiving the injection should be examined and the associated lymph nodes should be evaluated.

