Axillary (underarm) swelling or tenderness ipsilateral to the side of injection	None	No interference with activity	Repeated use of over-the-counter (non-narcotic) pain reliever > 24 hours or some interference with activity	Any use of prescription (narcotic) pain reliever or prevents daily activity	Emergency room visit or hospitalization
Headache	None	No interference with activity	Repeated use of over-the-counter pain reliever > 24 hours or some interference with activity	Significant; any use of prescription pain reliever or prevents daily activity	Requires emergency room visit or hospitalization
Fatigue	None	No interference with activity	Some interference with activity	Significant; prevents daily activity	Requires emergency room visit or hospitalization
Myalgia (muscle aches all over body)	None	No interference with activity	Some interference with activity	Significant; prevents daily activity	Requires emergency room visit or hospitalization
Arthralgia (joint aches in several joints)	None	No interference with activity	Some interference with activity	Significant; prevents daily activity	Requires emergency room visit or hospitalization

Reaction	Grade 0	Grade 1	Grade 2	Grade 3	Grade 4
Nausea/vomiting	None	No interference with activity or 1-2 episodes/ 24 hours	Some interference with activity or > 2 episodes/24 hours	Prevents daily activity, requires outpatient intravenous hydration	Requires emergency room visit or hospitalization for hypotensive shock
Chills	None	No interference with activity	Some interference with activity not requiring medical intervention	Prevents daily activity and requires medical intervention	Requires emergency room visit or hospitalization
Fever (oral)	< 38.0°C < 100.4°F	38.0 – 38.4°C 100.4 – 101.1°F	38.5 – 38.9°C 101.2 – 102.0°F	39.0 – 40.0°C 102.1 – 104.0°F	> 40.0°C > 104.0°F

Any solicited AR that meets any of the following criteria must be entered into the participant's source document and must also be recorded by the study site staff on the solicited AR page of the participant's eCRF:

- Solicited local or systemic AR that results in a visit to a healthcare provider (HCP), to be recorded as an MAAE ([Section 7.4.4](#)).
- Solicited local or systemic AR leading to the participant withdrawing from the study or the participant being withdrawn from the study by the investigator (AE leading to withdrawal).
- Solicited local or systemic AR lasting beyond 7 days post-injection.

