8.5.4. Safety Analyses

All safety analyses are descriptive in nature and will be based on the Safety Set, except summaries of solicited ARs, which will be based on the Solicited Safety Set. All safety analyses will be provided by study arm.

Safety and reactogenicity will be assessed by clinical review of all relevant parameters including solicited ARs (local and systemic ARs), unsolicited AEs, treatment-related AEs, severe AEs, SAEs, MAAEs, AESI, AEs leading to withdrawal, vital sign measurements, and physical examination findings.

The number and percentage of participants with any solicited local AR, with any solicited systemic AR, with any solicited AR during the 7-day follow-up period after each vaccination, and with Grade 3 or higher solicited AR will be provided. A 2-sided 95% exact CI using the

Clopper-Pearson method will be provided for the percentage of participants with any solicited AR.

The number and percentage of participants with unsolicited AEs, treatment-related AEs, severe AEs, SAEs, MAAEs, AESI, and AEs leading to withdrawal will be summarized. Unsolicited AEs will be presented by MedDRA system organ class and preferred term. Unsolicited AEs will be coded according to the MedDRA Dictionary for Adverse Reaction Terminology.

The number of events of solicited ARs, unsolicited AEs/SAEs, MAAEs, AEs leading to withdrawal, and AESI will be reported in summary tables accordingly. Pregnancy outcomes will also be summarized.

Table 16 summarizes the analysis strategy for safety parameters. For all other safety parameters, descriptive summary statistics will be provided. Further details will be described in the SAP.

Table 16: Analysis Strategy for Safety Parameters

Safety Endpoint	Number and Percentage of Participants, Number of Events	95% CI for Each Study Arm
Any Solicited AR (overall and by local, systemic)	X	X
Any Unsolicited AE	X	—
Any SAE	X	—
Any Unsolicited MAAE	X	—
Any Unsolicited AESI	X	—
Any Unsolicited Treatment-Related AE	X	—
Any Treatment-Related SAE	X	—
Any Unsolicited AE Leading to Withdrawal from Study Participation	X	—
Any Severe Unsolicited AE	X	—
Any Treatment-Related Severe Unsolicited AE	X	—

Abbreviations: AE = adverse event; AESI = adverse event of special interest; AR = adverse reaction;

CI = confidence interval; MAAE = medically attended adverse event; SAE = serious adverse event.

Notes: 95% CI using the Clopper-Pearson method, X = results will be provided.

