- SRR difference between mRNA-1273.222 and mRNA-1273 against the ancestral SARS-CoV-2 D614G at Day 29

Part J

Booster dose of mRNA-1273.815 (50 µg) or mRNA-1273.231 (50 µg) for participants who previously received a primary series of mRNA vaccine, a first booster dose of a monovalent mRNA vaccine, and a second booster dose of a bivalent mRNA vaccine against SARS-CoV-2:

- Antibody response of mRNA-1273.815 (50 µg) and mRNA-1273.231(50 µg) against SARS-CoV-2 Omicron BA.4/BA.5, BQ.1.1, and XBB.1.5 subvariants by GMT, geometric mean fold rise (GMFR), and SRR at Day 15 and Day 29

The primary safety objective will be evaluated by the following endpoints for all study parts (A.1, A.2, B, C, D, E, F, G, H and J):

- Solicited local and systemic reactogenicity adverse reactions (ARs) during a 7-day follow-up period after vaccination

- Unsolicited adverse events (AEs) during the 28-day follow-up period after vaccination
- Serious AEs (SAEs), medically attended AEs (MAAEs), AEs leading to withdrawal and AEs of special interest (AESIs) from Day 1 to end of study

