6.3.1.2. TEAEs by System Organ Class and Preferred Term

The following summary tables of TEAEs will be provided by SOC and PT using frequency counts and percentages (i.e., number and percentage of subjects with an event), up to 28 days after vaccination. Select TEAEs that will be collected throughout the study will also be summarized throughout the study when applicable:

- All unsolicited TEAEs
- All unsolicited TEAEs that are treatment-related

- All serious TEAEs
- All serious TEAEs that are treatment-related
- All unsolicited TEAEs leading to discontinuation from participation in the study
- All unsolicited severe TEAEs
- All unsolicited severe TEAEs that are treatment-related
- All unsolicited medically-attended TEAEs
- All unsolicited medically-attended TEAEs that are treatment-related
- All unsolicited AESIs
- All unsolicited AESIs that are treatment-related

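### Solicited reactions that the protocol classes as medically attended AEs or AEs leading to withdrawal have no place in the tables for those two primary safety components

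*SAP*

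**What the plan says.** **Endpoint.** SAP 3.1 gives one primary safety endpoint for all parts. Besides solicited reactions and 28-day unsolicited AEs, it names "Serious AEs (SAEs), medically attended AEs (MAAEs), AEs leading to withdrawal and AEs of special interest (AESIs) from Day 1 to end of study". The protocol's objective tables say the same. Neither limits MAAEs or withdrawals to unsolicited events. In Parts A.1, B, C and D, safety is the only primary objective.

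**Recording.** Protocol 7.4.3 lists solicited reactions that need an eCRF entry. The list includes "Solicited local or systemic AR that results in a visit to a healthcare provider (HCP), to be recorded as an MAAE" and "Solicited local or systemic AR leading to the participant withdrawing from the study", and the second carries the label of an AE leading to withdrawal. Such reactions go into the source document and "must also be recorded by the study site staff on the solicited AR page" of the eCRF.

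**Analysis.** SAP 6.3.1.1 has the row "Any unsolicited medically-attended TEAEs" and a withdrawal row and listing with the same limit. SAP 6.3.1.2 repeats the limit by system organ class and preferred term: "All unsolicited medically-attended TEAEs". Protocol Table 16 has "Any Unsolicited MAAE" and a withdrawal row that is also unsolicited only. The serious and fatal rows in SAP 6.3.1.1 carry no such limit.

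**The concern.** An event that the protocol tells sites to record as an MAAE, or as an AE leading to withdrawal, should reach the table that reports that class. Here the route appears to be cut by the single word unsolicited.

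The reactions affected are of particular interest. They were troublesome enough to send a participant to a provider or out of the study, and protocol 7.4.3 treats every solicited reaction as caused by the vaccine. If they are absent, a reader who takes the MAAE row as the rate of medically attended events after a booster reads a figure that is too low. The treatment-related MAAE row is affected most directly, because every missing event would belong in it. Under the SAP's introduction the SAP governs where methods differ, so the unrestricted wording of protocol 7.4.3 does not restore the events.

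**Working it through.** The point is a conflict of text, so the check follows one kind of event through both documents. Take a reaction on the solicited list that starts on Day 2, is entered in the eDiary, and leads to an urgent-care visit without an overnight stay.

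1. **Is it an MAAE?** Yes, under protocol 7.4.3. It is entered on the solicited-reaction page.
2. **Is it an unsolicited AE?** No. Protocol 7.4.1 and the glossary treat a listed reaction as unsolicited only if it starts outside the 7-day window, and Day 2 is inside.
3. **Is it an SAE?** Not on these facts. Protocol 7.4.2 generally takes inpatient hospitalization to mean at least one overnight stay. The unrestricted serious rows do not pick it up.
4. **Does it enter SAP 6.3.1.1 or 6.3.1.2 as an MAAE?** No. The MAAE rows, any and treatment-related, take unsolicited events only.
5. **Does it enter protocol Table 16 as an MAAE?** No, for the same reason.
6. **Where is it reported?** In SAP 6.3.2.1, by severity grade, onset day, duration and persistence beyond 7 days. None of these summaries is split by medical attendance or withdrawal. They use the Solicited Safety Set, whereas the AE tables use the Safety Set.

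If the reaction leads to withdrawal instead, steps 2 to 6 run the same way against the withdrawal rows. The one addition is the disposition summary in SAP 6.2.1, which gives the reason for discontinuation.

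The loss therefore needs all of these conditions: a listed reaction, onset within 7 days, capture in the eDiary, not serious, and a provider visit or a withdrawal. A reaction first reported by telephone or at a visit, and not already in the eDiary, must be entered as an unsolicited event under protocol 7.1.1, so it does reach the AE tables.

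**Size.** The documents give no rate of care-seeking for solicited reactions. Purely as an illustration, let p be the share of participants who meet the conditions for a provider visit and are not already in the MAAE row through another event. The number missing from an arm of size n is n × p. The assumed range for p is 0.5% to 2%, which has no source in the documents:

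- n = 375: 375 × 0.005 = 1.9, and 375 × 0.02 = 7.5
- n = 584: 584 × 0.005 = 2.9, and 584 × 0.02 = 11.7

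These figures show only what the assumption implies. They do not estimate the shortfall.

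**The case against.** The strongest reply is that little information is lost and that the SAP does what the protocol's analysis table asks.

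- **The SAP follows Table 16.** It does. Protocol 7.4.4 also speaks only of reviewing unsolicited AEs for MAAEs. A reader might infer that the SAP departs from an otherwise consistent protocol, and the documents do not support that. The protocol conflicts with itself: 7.4.3, the endpoint and the text above Table 16 carry no limit on these classes, while Table 16 and 7.4.4 do. Both documents need the correction.
- **The reactions are still reported.** A reader might infer that they vanish from the report, and that too would be wrong. Serious cases stay in the serious rows, and withdrawals appear in disposition. In protocol Table 14, Grade 4 is defined by an emergency room visit or hospitalization for 8 of the 11 reactions, so the Grade 4 column shows much of the emergency care. Grade does not identify other visits, though: a Grade 2 or 3 reaction seen at urgent care looks the same as one managed at home.
- **A second record may exist on the AE page.** Neither document provides for one, and the eCRF is not in the documents. If sites do make such an entry, a table built from that page might include it, although protocol 7.4.1 would still not make the event unsolicited.
- **The conflict could be settled the other way**, by restating the endpoint as unsolicited MAAEs and withdrawals, with solicited reactions as their own component. That would be coherent, but it narrows a primary endpoint and leaves the 7.4.3 recording rule with no analysis behind it.

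A further inference concerns protocol 7.1.5, which says "Any clinically significant finding identified during a study visit should be reported as an MAAE". It is tempting to read this as counting scheduled-visit findings that needed no medical attention. The text does not say scheduled, and it is limited to clinically significant findings. What stands is only that it describes an MAAE differently from 7.4.4, which requires an unscheduled visit to a provider.

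**Conclusion.** The point holds within the conditions set out above. Non-serious solicited reactions that start within 7 days, are captured in the eDiary, and are medically attended or cause withdrawal belong to two components of the primary safety endpoint, yet they are absent from the rows that report those components. Against the classes that 7.4.3 defines, the any and treatment-related MAAE rates, and the AE-withdrawal rate, err low whenever such a participant exists.

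The amount cannot be sized from the documents, and the illustrative counts should not be quoted as a finding. Safety analyses are descriptive, so no hypothesis test, alpha or power is touched. The conclusion assumes that the tables are programmed as written and that no parallel AE-page record feeds them. The correction is worth making because the gap lies in a primary endpoint and is cheap to close.

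**What to change.** In SAP 6.3.1.1, SAP 6.3.1.2 and protocol Table 16, define the MAAE and AE-leading-to-withdrawal rows, any and treatment-related, as unsolicited TEAEs plus solicited reactions recorded under protocol 7.4.3 as medically attended or leading to withdrawal. Show the two sources as sub-rows, and count each participant once in the combined row. Extend the withdrawal listing in SAP 6.3.1.1 in the same way. Align protocol 7.4.4 so that solicited reactions are also reviewed for MAAEs.

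Separately, reconcile protocol 7.1.5 with 7.4.4 so that one description of an MAAE applies throughout.

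The cost is wording in both documents and table programming. The entries come from a page that 7.4.3 already requires sites to complete, so no new data should be needed, provided that the page identifies the reason for entry; this should be checked against the eCRF. The downside for the sponsor is slightly less favourable MAAE and withdrawal percentages.

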At the dosing visit on Day 1, participants will be instructed how to document and report solicited ARs within a provided electronic diary (eDiary). Solicited ARs will be assessed for 7 days (the day of injection and the following 6 days), and unsolicited AEs will be assessed for 28 days after injection; SAEs, MAAEs, AEs leading to withdrawal, pregnancies and AESI will be assessed throughout the study. All participants will be tested for the presence of SARS-CoV-2 antibodies at baseline and at Day 29 (primary immunogenicity endpoint). Participants in Part J will also be tested for the presence of SARS-CoV-2 antibodies at Day 15 (primary immunogenicity endpoint). Additional blood draws will be collected on Day 91 (Parts A.2, F, G, H, and J only), Day 181, and Day 366 (Parts A.1, B, C, D, F, and G only). In addition, active surveillance for intercurrent or breakthrough SARS-CoV-2 infection will occur throughout the study and reported as AEs (confirmed symptomatic infections will be reported as MAAEs if not SAEs). Participants with signs and symptoms meeting the CDC case definition for COVID-19 (21 February 2021 or most recent [[CDC 2020](#)]) will be asked to contact the site and undergo prompt assessment which will include RT-PCR testing (of a respiratory sample) to assess symptomatic COVID-19. Participants with any clinical or radiographic evidence of pneumonia will also undergo RT-PCR testing. Suspected COVID-19 cases will also be tested using a multiplex assay to assess for non-SARS-CoV-2 causes of upper or lower respiratory tract infection ([Table 12](#) and [Table 13](#)). Participants will have blood samples collected at scheduled study site visits during the study for immunogenicity assessments or other medical concerns according to the investigator's judgment.

Participants may experience AEs, to include symptoms of COVID-19, that necessitate an unscheduled visit. There may also be situations in which the investigator asks a participant to report for an unscheduled visit following the report of an AE. Additional examinations may be conducted at these visits as necessary to ensure the safety and well-being of participants during the study. Electronic case report forms should be completed for each unscheduled visit. In addition, participants may have blood samples collected at unscheduled visits for acute respiratory symptoms.

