7.4.4. Medically Attended Adverse Events

An MAAE is an AE that leads to an unscheduled visit to an HCP. This would include visits to a study site for unscheduled assessments (eg, abnormal laboratory follow-up, COVID-19 [[Section 7.1.6](#)]) and visits to HCPs external to the study site (eg, urgent care, primary care physician). Investigators will review unsolicited AEs for the occurrence of any MAAEs. Unsolicited AEs will be captured on the AE page of the eCRF.

All confirmed COVID-19 cases will be recorded as MAAEs.

All suspected cases of anaphylaxis should be recorded as MAAEs and reported as an SAE, based on the criteria for a medically important event, unless the event meets other serious criteria. As an SAE, the event should be reported to the Sponsor or designee immediately and in all circumstances within 24 hours per [Section 7.4.11](#). The investigator will submit any updated anaphylaxis case data to the Sponsor within 24 hours of it being available. For reporting

purposes, a participant who displays signs or symptoms consistent with anaphylaxis (as follows) should be reported as a potential case of anaphylaxis. This is provided as general guidance for investigators and is based on the Brighton Collaboration case definition ([Rüggeberg et al 2007](#)).

Anaphylaxis is an acute hypersensitivity reaction with multi-organ system involvement that can present as, or rapidly progress to, a severe life-threatening reaction. It may occur following exposure to allergens from a variety of sources.

Anaphylaxis is a clinical syndrome characterized by the following:

- Sudden onset AND
- Rapid progression of signs and symptoms AND
- Involves 2 or more organ systems, as follows:
 - **Skin/mucosal:** urticaria (hives), generalized erythema, angioedema, generalized pruritus with skin rash, generalized prickle sensation, and red and itchy eyes.
 - **Cardiovascular:** measured hypotension, clinical diagnosis of uncompensated shock, loss of consciousness or decreased level of consciousness, and evidence of reduced peripheral circulation.
 - **Respiratory:** bilateral wheeze (bronchospasm), difficulty breathing, stridor, upper airway swelling (lip, tongue, throat, uvula, or larynx), respiratory distress, persistent dry cough, hoarse voice, sensation of throat closure, sneezing, and rhinorrhea.
 - **Gastrointestinal:** diarrhea, abdominal pain, nausea, and vomiting.

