7.4.7. Eliciting and Documenting Adverse Events

The investigator is responsible for ensuring that all AEs and SAEs are recorded in the eCRF and reported to the Sponsor.

Solicited ARs will be collected from Day 1 through 7 days after vaccination. Other (unsolicited) AEs will be collected from Day 1 through 28 days after vaccination.

The MAAEs, AESI, AE leading to withdrawal, AESI, and SAEs will be collected from participants as specified in the SoE ([Table 17](#), [Table 18](#), [Table 19](#), and [Table 20](#)) until the end of their participation in the study. Any AEs occurring before receipt of IP will be analyzed separately from AEs occurring after receipt of the study vaccine.

At every study site visit or telephone contact, participants will be asked a standard question to elicit any medically related changes in their well-being (including COVID-19 symptoms) according to the scripts provided. Participants will also be asked if they have been hospitalized, had any accidents, used any new medications, changed concomitant medication regimens (both prescription and over-the-counter medications), or had any non-study vaccinations.

In addition to participant observations, physical examination findings, or other documents relevant to participant safety classified as an AE will be documented on the AE page of the eCRF.

After the initial AE/SAE report, the investigator is required to proactively follow each participant at subsequent visits/contacts. All AEs and SAEs will be treated as medically appropriate and followed until resolution, stabilization, the event is otherwise explained, or the participant is LTFU (as defined in [Section 6.3](#)).

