For calculation of antibody levels/titers, antibody values reported as below LLOQ will be replaced by $0.5 \times \text{LLOQ}$. Values that are greater than the upper limit of quantification (ULOQ) will be converted to the ULOQ if actual values are not available. Missing results will not be imputed unless specified otherwise.

The following **analysis periods for safety analyses** will be used:

- Up to 28 days after vaccination: from the day of vaccination (Day 1) and continues through the earliest date of (the day of vaccination and 27 subsequent days, the day of study discontinuation). This analysis period will be used as the primary analysis period for safety analyses including unsolicited AEs, except for solicited ARs, unless specified otherwise.
- Throughout the study: from the day of vaccination (Day 1) and continues through the earliest date of (study completion, discontinuation from the study, or death).

Unscheduled visits: Unscheduled visit measurements will be included in the analysis as follows:

- In scheduled visit windows per specified visit windowing rules.
- In the derivation of baseline/last on-treatment measurements.
- In the derivation of maximum/minimum on-treatment values and maximum/minimum change from baseline values for safety analyses.
- In individual subject data listings as appropriate.

Visit windowing rules: The analysis visit windows for protocol-defined visits are provided in [Appendix B](#).

Incomplete/missing data:

- Imputation rules for missing or incomplete days of medications, non-study vaccinations and procedures are provided in [Appendix C](#).
- Imputation rules for missing or incomplete AE dates are provided in [Appendix D](#).
- If the laboratory results are reported as below the LLOQ (e.g., <0.1), the numeric values will be imputed by $0.5 \times \text{LLOQ}$ for the calculation of summary values. If the laboratory results are reported as greater than the ULOQ (e.g., >3000), the numeric values will be imputed by ULOQ in the summary if actual values are not available.
- Other incomplete/missing data will not be imputed, unless specified otherwise.

Treatment groups

- Part A.1: 50 µg of mRNA-1273.211 and 100 µg of mRNA-1273.211
- Part A.2: 50 µg of mRNA-1273.214
- Part B: 100 µg of mRNA-1273
- Part C: 50 µg of mRNA-1273.617.2 and 100 µg of mRNA-1273.617.2
- Part D: 50 µg of mRNA-1273.213 and 100 µg of mRNA-1273.213
- Part E: 100 µg of mRNA-1273.213
- Part F Cohort 1: 50 µg of mRNA-1273.529

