6.3.1. Adverse Events

A treatment-emergent AE (TEAE) is defined as any event occurring during the study not before exposure to study vaccine or any event already present that worsens after exposure to study vaccine. [Note: worsening of a pre-existing condition after vaccination will be reported as a new AE.]

Adverse events will also be evaluated by the investigator for the coexistence of MAAE which is defined as an AE that leads to an unscheduled visit to a healthcare practitioner.

Overview of unsolicited AEs will be summarized by stage, up to 28 days after vaccination and throughout the study (see [Section 6.1](#)).

All summary tables (except for the overall summary of AEs) for unsolicited AEs will be presented by SOC and PT for TEAEs with counts of subjects included. SOC will be displayed in internationally agreed order. PT will be displayed in alphabetical order for first booster, in descending order of frequency based on the mRNA-1273 50 µg group then alphabetically for second booster, and in descending order of frequency based on the mRNA-1273.231 50 µg group then alphabetically for third booster. When summarizing the number and percentage of subjects with an event, subjects with multiple occurrences of the same AE or a continuing AE will be counted once. Subjects will be presented according to

the highest severity in the summaries by severity, if subjects reported multiple events under the same SOC and/or PT.

Percentages will be based upon the number of subjects in the Safety Set.

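### Whole-study medically attended AE percentages in the second-booster tables mix about 6 and about 12 months of follow-up and include COVID-19, with no common-window or person-time version planned

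*SAP*

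**What the plan says.** **Endpoint.** SAP 3.1 makes these part of the primary safety endpoints in every Part: "Serious AEs (SAEs), medically attended AEs (MAAEs), AEs leading to withdrawal and AEs of special interest (AESIs) from Day 1 to end of study".

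**What enters the count.** Protocol 7.4.7 limits general reporting: "Other (unsolicited) AEs will be collected from Day 1 through 28 days after vaccination". COVID-19 is treated differently. Protocol 3.1 says that "active surveillance for intercurrent or breakthrough SARS-CoV-2 infection will occur throughout the study and reported as AEs", and Protocol 7.4.4 says "All confirmed COVID-19 cases will be recorded as MAAEs".

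**Periods.** SAP 6.1 defines two safety periods. Of the 28-day period it says: "This analysis period will be used as the primary analysis period for safety analyses including unsolicited AEs, except for solicited ARs". The whole-study period starts on Day 1 and "continues through the earliest date of (study completion, discontinuation from the study, or death").

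**Measure.** SAP 6.3.1.1 gives number and percentage of subjects for each category, including "Any unsolicited medically-attended TEAEs". On the denominator, SAP 6.3.1 says "Percentages will be based upon the number of subjects in the Safety Set". The overview is produced for both periods.

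**Length of follow-up.** Under SAP 6.2.1 a participant completes the study at 12 months in Parts A.1, B, C, D, E, F and G, and at 6 months in Parts A.2, H and J.

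**Table order.** SAP 6.3.1 orders preferred terms in the second-booster tables by their frequency in the mRNA-1273 50 µg group. SAP 6.2.3 and 6.2.4 use the same rule.

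**The concern.** A percentage of participants with at least one event rises with time at risk. If one table places 6-month and 12-month arms side by side, the 12-month arms will show more participants with an MAAE even when the underlying hazard is identical. The artefact has a direction. It makes the Part F mRNA-1273 comparator look worse and the 6-month candidates in Parts H and A.2 look better.

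COVID-19 adds a second, separate distortion. It is an MAAE by definition, it continues to be captured after Day 28, and its incidence depends on calendar time. SAP 6.4.3 notes that Part H enrolled in August 2022 and the Part F mRNA-1273 arm in February 2022.

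The SAP deals with both matters elsewhere. It requires a check of baseline and demographic characteristics before the Part H immunogenicity comparison (6.4.3), and it uses person-time rates for SARS-CoV-2 infection (6.5.2). Neither safeguard reaches the AE tables. What is at stake is how a reader interprets a descriptive table for a primary safety endpoint.

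**Working it through.** The plan states no figure for this point, so there is nothing to reproduce. The check has four steps.

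**1. Are the arms shown together?** Parts A.2, G and H contain no mRNA-1273 50 µg arm. Part F Cohort 2 is the only source of one in this study. A sort rule for second-booster tables based on that arm works only if the A.2, G and H arms stand beside it. This is an inference; the SAP does not say it outright.

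**2. Planned exposure** (arm sizes from SAP Table 2; days since injection from the Protocol schedules of events):
- Part H: 500 × 180/365 = 246.6 person-years, or 0.49 per participant.
- Part F mRNA-1273 50 µg: 375 × 365/365 = 375 person-years, or 1.00 per participant.
- Ratio of follow-up: 365/180 = 2.03.
- Six-month second-booster participants: A.2 300 + H 500 = 800. Twelve-month: F Cohort 2 750 + G 375 = 1,125. Share with six months: 800/1,925 = 41.6%.

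**3. Follow-up alone.** Assume the same constant hazard in both arms. Let a be the Part H risk to Day 181 and b the Part F risk to Day 366:
- b = 1 − (1 − a)^(365/180)
- 95% half-width of the difference = 1.96 × √[a(1 − a)/500 + b(1 − b)/375]

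| Assumed a | b | Gap (points) | Half-width (points) |
|---|---|---|---|
| 1% | 2.0% | 1.0 | 1.7 |
| 5% | 9.9% | 4.9 | 3.6 |
| 15% | 28.1% | 13.1 | 5.5 |

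The gap equals the half-width at a = 2.7%. Above that, identical arms would be expected to differ by more than sampling noise.

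Both remedies remove this gap. Restricted to onset through Day 181, both arms show 5% when a = 5%. For first-event rates with person-time stopping at the event, the hazard is −ln(0.95) × 365/180 = 0.104 per year:
- Part H: 25 events over 25/0.104 = 240 person-years.
- Part F: 37.0 events over 37.0/0.104 = 356 person-years.
- Both give 10.4 per 100 person-years.

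**4. COVID-19 alone.** Assume equal follow-up and independent events, with non-COVID risk p and COVID-19 risk c. The total MAAE risk is 1 − (1 − p)(1 − c), so the gap between arms is (1 − p) times the difference in c.
- With p = 20% and c = 10% against 20%, totals are 1 − 0.8 × 0.9 = 28% and 1 − 0.8 × 0.8 = 36%.
- A preferred-term table cannot recover p. The non-COVID count lies between the total minus COVID-19 and the total: 18% to 28% in the first arm and 16% to 36% in the second.
- With 500 against 375 participants, p from 5% to 30% and a lower-arm COVID-19 risk of 1% or 5%, the COVID-19 risks must differ by about 4 to 9 points before the gap exceeds the half-width.
- Over 28 days, an assumed 1% against 3% moves the total by only 1.4 to 1.9 points, with half-widths of 3.4 to 6.2. That is within noise.

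**The case against.** **More is planned than crude percentages.** A reader might infer from SAP 6.3.1.1 that nothing else will be reported. The documents do not support that. Protocol 8.5.4 and its Table 16 also plan numbers of events, including MAAEs. SAP 6.3.1.1 adds treatment-related counts in every category, which will normally exclude COVID-19. SAP 6.3.1.2 gives MAAEs by SOC and preferred term, and SAP 6.2.5 summarises study duration. These mitigate the problem, and approximate event rates could be formed from them. None of them, however, gives a common-window or exposure-adjusted participant summary, or the number of participants with a non-COVID MAAE. The treatment-related rows also rest on open-label judgement and still cover unequal follow-up.

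**Displays are by Part.** SAP 6.1 says summaries are provided by study arm for each Part, and planned follow-up is the same for all arms within a Part. This is the strongest objection. The sort rule answers it for the second-booster tables but does not settle it beyond doubt.

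**Scope.** A reader might extend the point to all non-randomised arms. That goes too far. First-booster arms are all planned for 12 months, and F Cohort 2 and G both have 12 months, so unequal follow-up does not arise there. Part J is randomised, with 6 months in both arms.

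**Nothing is tested.** Safety is descriptive, and the primary safety period is a common 28 days. This stands. The half-widths above are only a yardstick for when a gap would catch the eye. The Protocol also allows clearly identified ad hoc exploratory analyses in the CSR, so nothing would be lost for good.

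**Conclusion.** The concern holds in a limited form, as a cheap improvement. In the second-booster tables, whole-study MAAE percentages appear to set about 800 six-month participants beside about 1,125 twelve-month participants, with no planned summary that allows for the difference. The true size cannot be computed because the documents give no MAAE or COVID-19 rate. Under an equal constant hazard, follow-up alone would produce a gap beyond sampling noise once the 6-month risk exceeds about 2.7%, and a gap of 4.9 points at 5%.

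The conclusion rests on the inferred side-by-side display, planned arm sizes and follow-up, a constant hazard and, for COVID-19, independent events. It gives no reason to doubt the 28-day safety summary, Part J or any immunogenicity conclusion.

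**What to change.** In SAP 6.3.1.1, for the second-booster tables (A.2, F Cohort 2, G, H):

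1. For whole-study MAAEs, and likewise SAEs and AESIs, add one of the following beside the existing rows:
   - percentages restricted to onset through Day 181 in every arm; or
   - first-event incidence per person-year, with person-time stopping at the event as in SAP 6.5.2. The study-duration variable in SAP 6.2.5 does not stop at the event, so it is not the right denominator by itself.
2. Add one whole-study row for participants with any unsolicited medically attended TEAE, excluding a listed set of COVID-19 and SARS-CoV-2 infection preferred terms.
3. Label these rows supportive and descriptive. State that calendar-time differences between arms, including other seasonal illness, remain.

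No COVID-excluded row is needed for the 28-day period, since plausible differences there are within noise.

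The cost is some SAP wording, a preferred-term list, one simple derivation and a few extra table rows. No new data are needed and no existing row is removed.
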